	New dose step (mg/da	YJ	Reason for change
1	□ 25 □ 37.5		☐ Adverse event*
	□ 50 □ 62.5		☐ Patient's decision
(DD/WINN/1111)	□ Other: ⅃⅃		□ Doctor's decision
Uines may be added if the	haya haan mara sha	as)	Other, please state:
(Lines may be added if there			of the CDE
* In the event of an adverse	event, piease completo	e the safety section	of the CKF
Has treatment with sunitinih	heen interrunted (inter	rruntion > 7 consecu	tive days) since treatment initiation?
☐ Yes ☐ No	seen interrupteu (inter	Trapaon > 7 consecu	ave days) since treatment initiation:
If yes, please describe each in	nterruption:		

Table 3a – Temporary treatment interruptions (sunitinib)			
Start date of	Duration (days)	ration (days) If yes, reason for interruption	
interruption			
		☐ Adverse event*	
		\square Patient's decision	
(DD/MM/YYYY)		☐ Doctor's decision	
		☐ Other, please state	e:
(Lines may be added if there l			
* In the event of an adverse	event, please complet	e the safety section o	of the CRF
EVEROLIMUS screen -	Treatment continu	uad	
		ueu	
If treated with everolim			
	ose change since the la	ast tumour assessmer	nt visit on [date of last tumour assessment visit
entered]? ☐ Yes ☐ No			
If yes, please describe the ste			
Table 2b - Stepwise do		•	
Date	If yes, new dose step	(mg/day)	Reason for change
	□ 5		☐ Adverse event*
	□ 10		☐ Patient's decision
(DD/MM/YYYY)	☐ Other ☐☐		☐ Doctor's decision
			☐ Other, please state:
(Lines may be added if there l	have been more chang	es)	
* In the event of an adverse	event, please complet	e the safety section o	of the CRF
Has treatment with everolim	us been interrupted te	emporarily (interrupti	on > 7 consecutive days) since the last tumour
assessment visit on [date of la	ast tumour assessment	t visit entered]? 🛛 Y	'es □ No
If yes, please describe each ir	nterruption:		
Table 3b – Temporary	treatment interruptio	ns (everolimus)	
Start date o	f Duration (days)	If yes, reason for in	nterruption
interruption			•
	/	☐ Adverse event*	
		☐ Patient's decisio	n
(DD/MM/YYYY)		☐ Doctor's decision	n
		☐ Other, please sta	ate:
1 11 116.1	i		
(Lines may be added if there	have been more inter		
* In the event of an adverse	have been more interievent, please complet	ruptions)	

	EVEROLIMUS screen - New treatment line		
For all cases of treatment with everolimus initia	ted since the last doc	umented visit	
Treatment with everolimus initiated as:			
☐ Monotherapy			
☐ Combination therapy with:			

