☐ A somatostatin analogue Please state: ☐ Octreotide			
□ Lanreotide	;		
☐ Other treatment, please state	·o. 1)		
□ Other treatment, piease star	re: 1)		
Date of initiation:// (DD/N	1M/YYYY)		
Dose and dosage regimen: ☐ 5 mg/d	ау		
□ 10 mg/day			
☐ Other, please state: ☐☐ mg/day			
		2	
Has there been a stepwise change in dose since		? □ Yes □ No	
If yes, please describe the stepwise changes in d			
Table 2b - Stepwise dose changes (everolin			
Date New dose step (mg	/day)	Reason for change	
		☐ Adverse event*	
		☐ Patient's decision	
(DD/MM/YYYY) □ Other □□		☐ Doctor's decision	
		☐ Other, please state:	
(Lines may be added if there have been more cho			
* In the event of an adverse event, please comp	lete the safety section	n of the CRF	
Has treatment with everolimus been interrupted	(interruption > / cons	secutive days) since treatment initiation?	
☐ Yes ☐ No			
If yes, please describe each interruption:			
Table 3b – Temporary treatment interrupt			
Start date of Duration (days)	If yes, reason for i	nterruption	
interruption			
- - / - - / - -	☐ Adverse event*		
(DD (MM A) (MM))	☐ Patient's decision	I 1	
(DD/MM/YYYY)	☐ Doctor's decisio		
	☐ Other, please st	ate:	
(Lines may be added if there have been more into			
* In the event of an adverse event, please comp	lete the safety section	n of the CRF	
CHEMOTHERAPY screen - Treatment con	tinued		
If treated with chemotherapy:			
If treatment with chemotherapy has been initia	ted and continued as	a combination treatment since last visit:	
		ent visit on [date of last tumour assessment visit	
	e iast tuillour assessiii	ient visit on faate of last turnour assessment visit	
If yes, please describe the stepwise changes in d	entered]?		
Table 2c - Stepwise dose changes (chemotherapy)			
	therapy)	for shange	
Date Dose change	therapy) Reason	for change	
Date Dose change □	therapy) Reason □ Adver	rse event*	
Date Dose change	Reason Adver	rse event* nt's decision	
Date Dose change □	therapy) Reason Adver Patien Doctor	rse event* nt's decision or's decision	
Date Dose change □ / □ / □ Increase (DD/MM/YYYY) □ Decrease	therapy) Reason Adver Patier Doctor Other	rse event* nt's decision	
Date Dose change	Reason Adver Patier Doctor Other	rse event* nt's decision or's decision r, please state:	
Date Dose change □ / □ / □ Increase (DD/MM/YYYY) □ Decrease	Reason Adver Patier Doctor Other	rse event* nt's decision or's decision r, please state:	

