Date Dose change	Reason Adver Doctor Other	rse event* nt's decision or's decision r, please state: n of the CRF	
Date Dose change	Reason Adver Patier Docto Other Inges) Joseph Section Adver Adver Control Other Adver Adver Control Other C	rse event* nt's decision or's decision r, please state: n of the CRF an 7 consecutive days from the scheduled date of	

☐ Yes ☐ No		
If yes, reason for postponi	ng.	
☐ Adverse event*	116.	
☐ Patient's decision		
☐ Doctor's decision		
Other, please sta		plete the safety section of the CRF
in the event of an advers	se event, please com	piete the safety section of the CKF
CUENCEUEDADY		. 1.
CHEMOTHERAPY screen		
_		nitiated since the last documented visit
Treatment of: [Pre-comple	ted with the treatmer	it entered in 3.3]
Treatment initiated as:		
☐ Chemotherapy	•	
☐ Combination th		
	atostatin analogue	
Please	e state: 🗆 Octreotid	е
□ Oth an	☐ Lanreotide	1)
	treatment, please sta	
Data of initiation of the fire		2)(DD/MM/YYYY)
		J_/(UU/MINI/TYTY)
Number of cycles delivered	ı:	
Cycle schedule: ☐ 7 days	□ 14 days □ 21 day	rs □ 28 days □ other, please state: □□ days
1	_	treatment was started? ☐ Yes ☐ No
If yes, please describe the		
Table 2c - Stepwise de	 	
Date	Dose change	Reason for change
		☐ Adverse event*
(DD/MM/YYYY)	□ Increase	☐ Patient's decision
(BB/WINI/TTTT)	☐ Decrease	□ Doctor's decision
	 	Other, please state:
(Lines may be added if the		
* In the event of an adver	se event, please com	plete the safety section of the CRF
11 +	(+ + + - //	
	•	postponed by more than 7 consecutive days from the scheduled date of
treatment since initiation?		
If yes, reason for postponi		
If yes, reason for postponi ☐ Adverse event*	ng:	
If yes, reason for postponin ☐ Adverse event* ☐ Patient's decision	ng: n	
If yes, reason for postponing Adverse event* Patient's decision Doctor's decision	ng: n n	
If yes, reason for postponin ☐ Adverse event* ☐ Patient's decision ☐ Doctor's decision ☐ Other, please sta	ng: n n nte:	
If yes, reason for postponin ☐ Adverse event* ☐ Patient's decision ☐ Doctor's decision ☐ Other, please sta	ng: n n nte:	plete the safety section of the CRF
If yes, reason for postponin ☐ Adverse event* ☐ Patient's decision ☐ Doctor's decision ☐ Other, please sta	ng: n n nte:	plete the safety section of the CRF
If yes, reason for postponin ☐ Adverse event* ☐ Patient's decision ☐ Doctor's decision ☐ Other, please sta	ng: n n nte:	plete the safety section of the CRF

INTERFERON ALPHA screen - Treatment continued

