If treated with interferon alpha:
If treatment with Interferon alpha has been initiated and continued as a combination treatment since last visit:
Has there been a stepwise dose change since the last tumour assessment visit on [date of last tumour assessment visit
entered]? ☐ Yes ☐ No
If yes, please describe the stepwise changes in dose:
Table 2d - Stepwise dose changes (IFN-a)
Date Reason for change
☐ / ☐ Adverse event*
☐ Patient's decision
(DD/MM/YYYY) Doctor's decision
☐ Other, please state:
(Lines may be added if there have been more changes)
* In the event of an adverse event, please complete the safety section of the CRF
Has treatment with interferon alpha been postponed by more than 7 consecutive days from the scheduled date of
treatment since the last tumour assessment visit on [date of the last tumour assessment visit entered]?
☐ Yes ☐ No
If yes, reason for postponing:
☐ Adverse event
☐ Patient's decision
☐ Doctor's decision
☐ Other, please state:
* In the event of an adverse event, please complete the safety section of the CRF
INTERFERON ALBUA severe New treatment line
INTERFERON ALPHA screen - New treatment line
For all cases of treatment with interferon alpha initiated since the last documented visit
Treatment with interferon initiated as:
☐ Monotherapy
☐ Combination therapy with:
☐ A somatostatin analogue
Please state:
□ Lanreotide
☐ Other treatment, please state: 1)
2)
T (
Type of treatment: Pegylated
☐ Standard
D
Date of initiation:/ (DD/MM/YYYY)
Initial dose: ——— MIU/day
Has there been a stepwise change in dose since treatment was started? ☐ Yes ☐ No
If yes, please describe the stepwise changes in dose:
Table 2d - Stepwise dose changes (IFN-a)
Date Reason for change
☐☐ / ☐ Adverse event*
□ □ Patient's decision
(DD/MM/YYYY) Doctor's decision
☐ Other, please state:
(Lines may be added if there have been more changes)
* In the event of an adverse event, please complete the safety section of the CRF
•
Has treatment with IFN- α been postponed from more than 7 consecutive days from the scheduled date of treatment
since initiation? Yes No

If yes, reason for postponing: ☐ Adverse event* ☐ Patient's decision ☐ Doctor's decision ☐ Other, please state:	
	please complete the safety section of the CRF
visit:	n analogue: unalogue has been initiated and continued as a combination treatment since last
entered]? ☐ Yes ☐ No	ange since the last tumour assessment visit on [date of last tumour assessment visit
If yes, please describe the stepwise	

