5.7.1. Treatment Drop-outs and Documented Reasons for Dropping Out of the Study

The following parameters will be presented for each of the analysis groups (targeted therapy or other treatment) and for each treatment:

- Total duration of exposure since starting treatment (also shown for the reference set).
- Numbers and percentages of patients who had at least one documented discontinuation of treatment in the study. The results will be shown for incident patients, prevalent patients and then for all patients.
- Number of documented temporary discontinuations by patient in the study.

- Time to the first temporary discontinuation from inclusion into the study. The results will be shown for incident patients, prevalent patients and then for all patients.
- Reasons for temporary discontinuations.
- Durations of temporary discontinuations.
- Numbers and percentages of patients who discontinued treatment permanently.
- Time until permanent discontinuation from inclusion into the study. The results will be shown for incident patients, prevalent patients and then for all patients.
- Time until permanent discontinuation from inclusion. Results will be shown for incident patients, prevalent patients and then for all patients.
- Reason for permanent discontinuation.

The analyses of exposure to treatment will be described by treatment received at inclusion but also by treatment received at least once during the study (main treatment or as a combination). If the patient takes the same treatment on several occasions over different periods, the sum of the exposure periods will be calculated.

The analyses of temporary discontinuations will be described by main treatment received at inclusion but also by main treatment ongoing at the time of temporary discontinuation.

In addition, the total duration of exposure of the treatment at inclusion since it was started will be analysed by the ECOG index value at inclusion.

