9.4. Safety Data

9.4.1. Treatment Drop-outs and Reasons for Dropping Out Documented for the Study

Table 14.3.1.1: Total Duration of Exposure to the Main Treatment Received at the Inclusion Since Starting the Documented Treatment in the Study – Safety Analysis Set

		Targeted therapies (N=XX)	Other treatments (N=XX)	Total (N=XX)
Total duration of treatment exposure (months)	N	XX	XX	XX
	Missing data	XX	XX	XX
	Mean (SD)	XX.XX (X.XX)	XX.XX (X.XX)	XX.XX (X.XX)
	Median	XX.X	XX.X	XX.X
	[Min; Max]	[XX.X; XX.X]	[XX.X; XX.X]	[XX.X; XX.X]
	[Q1; Q3]	[XX.X; XX.X]	[XX.X; XX.X]	[XX.X; XX.X]
Total duration of treatment exposure (N(%))	N	XX	XX	XX
	Missing data	XX	XX	XX
	[0-3] months	XX (XX.X%)	XX (XX.X%)	XX (XX.X%)
	[3-6] months	XX (XX.X%)	XX (XX.X%)	XX (XX.X%)
	[6-12] months	XX (XX.X%)	XX (XX.X%)	XX (XX.X%)
	[12-24] months	XX (XX.X%)	XX (XX.X%)	XX (XX.X%)
	> 24 months	XX (XX.X%)	XX (XX.X%)	XX (XX.X%)

Total duration of exposure = (Date of last dose of treatment – Date of first dose of treatment +1)/30.4375.

For patients still on treatment at 2 years, the date of the last treatment dose used is the date of the last visit.

For patients who dropped out of the study, the date of the last treatment dose used is the date of the last visit.

Using the same template:

Table 14.3.1.2: Total Duration of Exposure to the Main Treatment Received at the Inclusion Since Starting the Documented Treatment in the Study – Reference Set

Table 14.3.1.3: Total Duration of Exposure to the Treatment Received at Least Once During the Study – Safety Analysis Set

Add the footnote: As the start/end dates of combinations reported during a treatment line are not available, the visit dates were used to calculate the duration of the combination treatments. Exposure to combinations is overestimated.

Table 14.3.1.4: Total Duration of Exposure to the Treatment Received at Least Once During the Study – Reference Set

Table 14.3.1.5: Temporary Discontinuations of the Main Treatment at Inclusion Documented in the Study – Safety Analysis Set

		Targeted therapies (N=XX)	Other treatments (N=XX)	Total (N=XX)
At least one temporary discontinuation	N	XX	XX	XX
	Missing data	XX	XX	XX
	Yes No	XX (XX.X%) XX (XX.X%)	XX (XX.X%) XX (XX.X%)	XX (XX.X%) XX (XX.X%)
Number of temporary discontinuations per patient	N	XX	XX	XX
	Missing data	XX	XX	XX
	Mean (SD)	XX.XX (X.XX)	XX.XX (X.XX)	XX.XX (X.XX)
	Median	XX.X	XX.X	XX.X
	[Min; Max]	[XX.X; XX.X]	[XX.X; XX.X]	[XX.X; XX.X]
	[Q1; Q3]	[XX.X; XX.X]	[XX.X; XX.X]	[XX.X; XX.X]

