Time to the first temporary discontinuation since inclusion	N	XX	NA	XX
(months)	Missing data	XX		XX
	Mean (SD)	XX.XX (X.XX)		XX.XX
	Median	XX.X		(X.XX) XX.X
	[Min; Max]	[XX.X; XX.X]		[XX.X; XX.X]
	[Q1; Q3]	[XX.X; XX.X]		[XX.X; XX.X]
Time to the first temporary discontinuation since inclusion (N(%))	N	XX	NA	XX
(4.(7.0))	Missing data]0-3] months]3-6] months > 6 months	XX XX (XX.X%) XX (XX.X%) XX (XX.X%)		XX XX (XX.X%) XX (XX.X%) XX (XX.X%)
Time to the first temporary discontinuation since inclusion	N	XX	NA	XX
(months) – incident patients	Missing data	XX	1112	XX
	Mean (SD)	XX.XX (X.XX)		XX.XX
	Median	XX.X		(X.XX) XX.X
	[Min; Max]	[XX.X; XX.X]		[XX.X; XX.X]
	[Q1; Q3]	[XX.X; XX.X]		[XX.X; XX.X]
Time to the first temporary discontinuation since inclusion	N	VV	NIA	-
(N(%)) – incident patients	N Missing data	XX	NA	XX
	Missing data]0-3] months]3-6] months > 6 months	XX XX (XX.X%) XX (XX.X%) XX (XX.X%)		XX XX (XX.X%) XX (XX.X%) XX (XX.X%)
Time to the first temporary discontinuation since inclusion (months) – prevalent patients	N	XX	NA	XX
(montas) - prevatent patients	Missing data	XX		XX
	2			

Table 14.3.1.5: Temporary Discontinuations of the Main Treatment at Inclusion Documented in the Study – Safety Analysis Set

		Targeted therapies (N=XX)	Other treatments (N=XX)	Total (N=XX)
	Mean (SD)	XX.XX (X.XX)		XX.XX (X.XX)
	Median	XX.X		XX.X
	[Min; Max]	[XX.X; XX.X]		[XX.X; XX.X]
	[Q1; Q3]	[XX.X; XX.X]		[XX.X; XX.X]
Time to the first temporary discontinuation since inclusion $(N(\%))$ – prevalent patients	N	XX	NA	XX
	Missing data [0-3] months [3-6] months > 6 months	XX XX (XX.X%) XX (XX.X%) XX (XX.X%)		XX XX (XX.X%) XX (XX.X%) XX (XX.X%)
Reasons for temporary discontinuations	N Missing data Adverse event Patient's choice Doctor's choice Other	XX XX XX (XX.X%) XX (XX.X%) XX (XX.X%)	XX XX XX (XX.X%) XX (XX.X%) XX (XX.X%) XX (XX.X%)	XX XX XX (XX.X%) XX (XX.X%) XX (XX.X%) XX (XX.X%)
Duration of temporary discontinuations (days)	N Missing data	XX XX	NA	XX XX
	Mean (SD)	XX.XX (X.XX)		XX.XX (X.XX)
	Median	XX.X		XX.X
	[Min; Max]	[XX.X; XX.X]		[XX.X; XX.X]
	[Q1; Q3]	[XX.X; XX.X]		[XX.X; XX.X]

For chemotherapies, interferons and somatostatin analogs, a difference of more than 7 consecutive days is deemed to be a temporary discontinuation.

Programmer note:

- For the variables "Time to first temporary discontinuation", N=number of patients with at least one temporary discontinuation.

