- For the variables "Reasons for temporary discontinuations" and "Duration of temporary discontinuations", N=number of temporary discontinuations.

Table 14.3.1.6: Temporary Discontinuations of the Main Treatment Received at Least Once During the Study – Safety Analysis Set

		Targeted therapies (N=XX)	Other treatments (N=XX)	Total (N=XX)
At least one temporary discontinuation	N	XX	XX	XX
At least one temporary discontinuation	Missing data	XX	XX	XX
	Yes	XX (XX.X%)	XX (XX.X%)	XX (XX.X%)
	No	,	,	,
	NO	XX (XX.X%)	XX (XX.X%)	XX (XX.X%)
Number of temporary discontinuations per patient	N	XX	XX	XX
	Missing data	XX	XX	XX
	Mean (SD)	XX.XX (X.XX)	XX.XX (X.XX)	XX.XX (X.XX)
	Median	XX.X	XX.X	XX.X
	[Min; Max]	[XX.X; XX.X]	[XX.X; XX.X]	[XX.X; XX.X]
	[Q1; Q3]	[XX.X; XX.X]	[XX.X; XX.X]	[XX.X; XX.X]
Reasons for temporary discontinuations	N	XX	XX	XX
1 3	Missing data	XX	XX	XX
	Adverse event	XX (XX.X%)	XX (XX.X%)	XX (XX.X%)
	Patient's choice	XX (XX.X%)	XX (XX.X%)	XX (XX.X%)
	Doctor's choice	XX (XX.X%)	XX (XX.X%)	XX (XX.X%)
	Other	XX (XX.X%)	XX (XX.X%)	XX (XX.X%)
Duration of temporary discontinuations (days)	N	XX	NA	XX
2 station of temporary discontinuations (days)	Missing data	XX	1.11	XX
	Mean (SD)	XX.XX (X.XX)		XX.XX (X.XX)
	Median	XX.X		XX.X
	[Min; Max]	[XX.X; XX.X]		[XX.X; XX.X]
	[Q1; Q3]	[XX.X; XX.X]		[XX.X; XX.X]

The temporary discontinuations were not recorded for patients on "Other" treatments shown in the "Other treatments" column.

Table 14.3.1.7: Permanent Discontinuations of the Treatment at Inclusion Documented in the Study – Safety Analysis Set

		Targeted therapies (N=XX)	Other treatments (N=XX)	Total (N=XX)
Permanent discontinuation	N Missing data Yes No	XX XX XX (XX.X%) XX (XX.X%)	XX XX XX (XX.X%) XX (XX.X%)	XX XX XX (XX.X%) XX (XX.X%)
Time to permanent discontinuation since inclusion (months)	N Missing data Mean (SD) Median [Min; Max] [Q1; Q3]	XX XX.XX (X.XX) XX.X [XX.X; XX.X] [XX.X; XX.X]	XX XX XX.XX (X.XX) XX.X [XX.X; XX.X] [XX.X; XX.X]	XX XX.XX (X.XX) XX.X [XX.X; XX.X] [XX.X; XX.X]

Table 14.3.1.7: Permanent Discontinuations of the Treatment at Inclusion Documented in the Study – Safety Analysis Set

		Targeted therapies (N=XX)	Other treatments (N=XX)	Total (N=XX)
Time to permanent discontinuation since inclusion (N(%))	N Missing data]0-1] months]1-2] months]2-3] months	XX XX XX (XX.X%) XX (XX.X%) XX (XX.X%)	XX XX XX (XX.X%) XX (XX.X%) XX (XX.X%)	XX XX XX XX (XX.X%) XX (XX.X%) XX (XX.X%)

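### The per-patient number of temporary discontinuations is an episode count for everolimus and sunitinib but capped at one per visit interval for chemotherapy, interferon and somatostatin analogues, so the column for other treatments can be understated and Total mixes two units

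*SAP*

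**What the plan says.** SAP 5.7.1 asks, by group and by treatment, for the "Number of documented temporary discontinuations by patient in the study". The shells of Tables 14.3.1.5 (main treatment at inclusion) and 14.3.1.6 (main treatment received at least once) in SAP 9.4.1 carry a row "Number of temporary discontinuations per patient" with mean, median, range and quartiles, filled for targeted therapies, other treatments and Total.

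The data come from the case report form appended to the protocol, section 3.3. For sunitinib there is a repeatable table, "Table 3a – Temporary treatment interruptions (sunitinib)", with start date, duration and reason; everolimus has the same. The instruction is "If yes, please describe each interruption". For interferon the form asks "Has treatment with interferon alpha been postponed by more than 7 consecutive days from the scheduled date", with a yes/no answer and tick boxes for the reason. Chemotherapy and somatostatin analogues have the same question, "postponed by more than 7 consecutive days from the scheduled date of" treatment. None of these three has a date, a duration or a repeat line. The radionuclide screens hold a cycle count and no interruption question.

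The footnote to Table 14.3.1.5 turns the yes/no answer into an event: "For chemotherapies, interferons and somatostatin analogs, a difference of more than 7 consecutive days is deemed to be a temporary discontinuation". The footnote to Table 14.3.1.6 adds: "The temporary discontinuations were not recorded for patients on 'Other' treatments shown in the 'Other treatments' column".

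**The concern.** The same row label covers two quantities. In the targeted-therapy column it is a number of episodes. In the other column it is a number of visit intervals in which at least one postponement was reported, and two postponements between visits become one. Total averages the two. The reasons row inherits the problem, because a programmer note sets its N to the number of temporary discontinuations.

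Treatment discontinuations and their reasons belong to the safety part of the primary objective (SAP 5.5). Protocol section 2 says the health authority asked for data on both targeted drugs in comparison with other treatments, so these columns will be read side by side.

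**Working it through.** **What each drug's screen can hold**

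| Treatment | Recorded at follow-up | Most that can be counted |
|---|---|---|
| Sunitinib, everolimus | Each interruption over 7 days, lines can be added | No cap |
| Chemotherapy, interferon, somatostatin analogue (continued) | One yes/no since the last visit | 1 per visit interval |
| Same drugs (new line) | One yes/no since initiation | 1 since initiation |
| Radionuclide therapy | Number of cycles | No question shown |

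**What the SAP does with it.** Duration (both tables) and time to first discontinuation (Table 14.3.1.5) are already NA for other treatments; the count and the reasons are not. The baseline shells do follow the form: Table 14.1.4.1.13 (sunitinib, template reused for everolimus) has a number of earlier discontinuations, while Tables 14.1.4.1.15 to 14.1.4.1.17 (chemotherapy, interferon, analogues) have only a yes/no. The prospective tables depart from that pattern.

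**Size.** The plan gives no figure to reproduce, so this is an illustration. Inputs from the documents: visits about every 2 to 3 months (protocol 5.2.1), 14-day and 28-day schedules among the options on the form, and 30.4375 days per month (SAP 4.7). Assumption: each scheduled administration has an independent probability p = 5%, 10% or 20% of being postponed by more than 7 days.

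- Administrations per interval: k = months × 30.4375 / cycle length
- True expected count per interval: k × p
- Recordable count per interval: 1 − (1 − p)^k
- Shortfall: 1 − recordable / true

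Example, 14-day cycles, 3-month visits, p = 10%: k = 91.3125 / 14 = 6.52; true count 0.652; recordable 1 − 0.9^6.52 = 0.497; shortfall 1 − 0.497 / 0.652 = 24%.

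| Schedule | Visits | k | p = 5% | p = 10% | p = 20% |
|---|---|---|---|---|---|
| 14 days | 2 months | 4.35 | 8% | 15% | 29% |
| 14 days | 3 months | 6.52 | 13% | 24% | 41% |
| 28 days | 2 months | 2.17 | 3% | 6% | 12% |
| 28 days | 3 months | 3.26 | 6% | 11% | 21% |

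Rounding k down to whole administrations gives similar or smaller values (for 14 days and 3 months, k = 6: 12%, 22%, 39%). The model ignores that a delay of over a week leaves room for fewer cycles in the interval, so the upper values for 14-day cycles are on the high side.

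**The case against.** A reader might infer that the count for other treatments is always too low and that targeted therapy looks worse by construction. The documents do not support that. With no postponement or one per interval the two units agree, and the postponement rate is not given. The rule also counts a delay from the scheduled date as a discontinuation, which could push the count for other treatments up. The net direction between columns is not shown.

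A reader might also infer that patients who were never asked enter as zero. The SAP does not say so. Both count rows have a line for missing data, and SAP 4.5 generally leaves missing values out and reports their number. Nor does the gap for drugs coded as Other touch Table 14.3.1.5: the treatment at inclusion must be one of six named classes, so those drugs can appear only in Table 14.3.1.6, where the footnote discloses it. Radionuclide therapy is the class left unmentioned. SAP section 8 lists a sixth discontinuation variable, PTST2YN, whose meaning is not given; it should be checked before radionuclide data are declared absent.

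On importance, this is one descriptive row. Protocol 8.3.2.1 names proportions as the safety quantities to estimate, the documents disclaim strict comparisons between groups, and within a single drug the unit is consistent. A footnote would cure much of the labelling problem.

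All of this limits the point. It does not remove the pooled Total, which averages episodes with visit intervals, or a column label that promises a count the form cannot supply.

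**Conclusion.** The point holds in a limited form. For chemotherapy, interferon and somatostatin analogues the printed count is at most one per visit interval, or one since initiation on a new-line screen. It is understated whenever two or more postponements fall in the same interval. Total and the reasons row mix two units. The row for at least one discontinuation is not affected by the cap.

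The size depends on assumed postponement rates, independence between cycles and the visit interval: from about 3% (28-day schedule, 2-month visits, p = 5%) to about 41% (14-day cycles, 3-month visits, p = 20%). No corrected episode count can be recovered, because the repeat events were not collected.

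**What to change.** In Tables 14.3.1.5 and 14.3.1.6, choose one of two options for the count row:

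- set it to NA for other treatments and Total, as duration already is for other treatments; or
- replace it in every column by the number of visit intervals with at least one interruption or postponement of more than 7 days, collapsing the everolimus and sunitinib episodes to that unit.

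With either option:

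- base the reasons row for other treatments on intervals with a postponement;
- label the yes/no row for chemotherapy, interferon and analogues as postponement of more than 7 days;
- in Table 14.3.1.5, report radionuclide patients as not collected and leave them out of the denominator, once PTST2YN has been checked;
- extend the Table 14.3.1.6 footnote to radionuclide therapy;
- reconcile the threshold: the baseline shells for these drugs say at least 7 days, while the form and the Table 14.3.1.5 footnote say more than 7.

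The cost is a change to shells and footnotes using data already collected. One descriptive row is lost or made coarser.
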